## **7.4.2 Timing of Evaluations**

### **7.4.2.1 Entry Evaluations (Week 0 Visit)**

Subjects diagnosed with acute HIV infection must begin treatment within 72 hours after randomization, and preferably within 24 hours. Subjects randomized to Arm 1 must begin treatment within 72 hours after randomization, and preferably within 24 hours.

### **7.4.2.2 On-Study Evaluations**

On-study evaluations will occur according to the schedule of events as specified in Section 7.4.1. On-study evaluations will occur according to the schedule of events as specified in Section 7.4.1. according to whether the participant was enrolled before or after the approval of Amendment 1, of this protocol. A study visit will be considered missed if it is not completed before half of the time between the current and next study visit has elapsed.

. Study visit windows will be +/- 5 days for scheduled study visits.

### **7.4.2.3 Evaluations for Subjects Randomized to Arm 1 Who Do Not Start Study Treatment**

Subjects with recent HIV infection randomized to Arm 1 (immediate treatment) who do not start study treatment will be followed according to the originally specified schedule of evaluations.

### **7.4.2.4 Evaluations for Subjects Who Start Treatment without Meeting Eligibility Criteria**

Subjects with recent HIV infection randomized to Arm 2 (deferred treatment to be started at 24 weeks after HIV-1 diagnosis) who elect to start treatment despite not meeting criteria for treatment initiation will be invited to continue to be followed according to the originally specified schedule of evaluations. Study medication will not be provided to these subjects. The ART treatment will not be provided by the study in this case.

### **7.4.2.5 Premature Treatment Discontinuation Evaluation Provided by the Study**

Subjects who voluntarily discontinue treatment provided by the study will be advised to continue anti-retroviral treatment with public or private sources. The study investigators will take necessary steps to ensure that the subjects continue ART. Counseling will be provided with a special emphasis on safety, and later efficacy options to use in the future if the participant decides to discontinue ART provided by the study and not continue with any other. All the participants will be invited to continue with the follow-up evaluations according to the originally specified "Timing of Visits".

### **7.4.2.6 Premature Study Discontinuation Evaluations and Voluntary Treatment Provided by the Study**

Subjects who elect to withdraw from participation in the study prior to completion of the study will have all final evaluations performed for the end of the study as described in visit for Week 48.

### **7.4.3 Definitions of Evaluations and Special Instructions**

#### **7.4.3.1 Medical History**

A medical history must be present in source documents. The medical history should be comprehensive and include HIV-1 related and non-related diagnoses. Details of acute HIV seroconversion signs and symptoms and HIV risk behaviors should be included. Any allergies to any medications and their formulations must be documented.

#### **7.4.3.2 Medication History**

A medication history must be present in source documents, including any history of antiretroviral medication, immune-based therapy, or HIV-1-related vaccines, including blinded study medications.

All prescription medications taken within 30 days prior to study entry, including actual or estimated start and stop dates, should be included in both the source documents and on the case report forms (CRFs).

All nonprescription medications taken within 30 days prior to study entry, including actual or estimated start and stop dates, should also be included in source documents.

#### **7.4.3.3 Concomitant Medications**

All concomitant medications taken since the last report must be recorded in the source documents and CRFs and must include start dates and stop dates.

#### **7.4.3.4 Study Treatment Modifications**

All modifications to study drug(s) including initial doses, subject-initiated and/or protocol-mandated interruptions, modifications, and permanent discontinuation of treatment must be recorded at each visit in the source documents and CRFs.

#### **7.4.3.5 Clinical Assessments**

##### **1. Complete physical exam**

A complete physical exam is to be performed at study entry and study completion.

##### **2. Targeted physical exam**

A targeted physical examination is required as clinically indicated.

##### **3. Height to be collected at study entry.**

##### **4. Weight to be collected at all study visits.**

##### **5. Vital signs**

Oral temperature, pulse, and blood pressure to be collected at all visits.

**6. Signs and symptoms**

All signs, symptoms, and toxicities at entry must be documented in the subject's record and on the CRFs. Unless otherwise specified, after entry, only grade  $\geq 3$  and all signs and symptoms that led to a change in treatment, regardless of grade, must be recorded on the CRFs. The "Division of AIDS Table for Grading the Severity of Adult and Pediatric Adverse Events Version 1.0, December, 2004; Clarification August 2009" must be used and is available at <http://rsc.tech-res.com/safetyandpharmacovigilance>

**7. Tuberculosis screening**

Potential participants will be taken to a nearby clinic for TB screening (sputum acid fast bacilli stain and chest X-ray). Chest X-rays will be offered as part of the study procedures. Tuberculosis prophylaxis will be provided to participants according to Ministry of Health of Peru guidelines.

**8. Leukapheresis procedure**

A subset of SABES? participants ( $N = 40$ ) will undergo leukapheresis. There is a separate consent form and only those who are newly enrolled and volunteer for this procedure will have it performed. Qualitative assessment of the HIV reservoir (including its localization in different CD4 $^{+}$  T cell subsets) will require large numbers of cells, which is important as both size and distribution of the HIV reservoir will be key factors in strategies to induce a functional cure. Thus, we will use leukapheresis to collect large samples at critical time points (baseline, 24 and 48 weeks).

**9. Diagnoses**

All confirmed and probable diagnoses made since the last visit must be recorded in the source documents and CRFs. The following diagnoses will be recorded in source documentation and CRFs: U.S. Center for Disease Control and Prevention Category B and C diagnoses, major organ disease including but not limited to diabetes, cardiovascular disease and stroke, hepatitis, avascular necrosis, fat redistribution including central fat accumulation and peripheral fat wasting (as noted by subject and site staff and/or primary care provider). Please refer to AIDS Clinical Trials Group Appendix 60 for specific diagnoses and definitions which can be found at <http://www.hptn.org/web%20documents/HPTN052/Appendix60V1.123Feb2007.pdf>.

**7.4.3.6 *Laboratory Evaluations***

The "Division of AIDS Table for Grading the Severity of Adult and Pediatric Adverse Events Version 1.0, December, 2004; Clarification August 2009" must be used and is available at <http://rsc.tech-res.com/safetyandpharmacovigilance>.

All laboratory values must be documented in the subject's record and recorded on the CRFs. Subsequently, all laboratory values must be documented in the subject's record, but unless otherwise specified, only laboratory values Grade  $\geq 3$  must be recorded on the CRFs. Any laboratory toxicity that led to a change in treatment, regardless of grade, must be recorded on the CRFs. Laboratory evaluations that do not have a grading scale in the "Division of AIDS Table for Grading the Severity of Adult and Pediatric Adverse Events Version 1.0, December, 2004; Clarification August 2009" must be collected on the CRFs if the values are outside the upper or lower limit of normal. All values for total HDL and LDL cholesterol, and triglycerides should be recorded on the CRFs at baseline and every 12 weeks, regardless of toxicity grade.

1. Hematology

Hemoglobin, white blood cell count, absolute neutrophil count, platelets;

2. Blood chemistries

Serum amylase, lipase, bicarbonate, phosphorus, creatinine, AST (SGOT), ALT (SGPT), alkaline phosphatase.

3. Lipid panel

Subjects should be fasting for at least 8 hours when possible. Triglycerides, total cholesterol, HDL, LDL;

4. Urinalysis

Dipstick, and microscopic exam if dipstick positive;

5. Hepatitis B serology

Potential participants will be tested for hepatitis B infection through HBsAg, anti-HBc and anti-HBs. The interpretation of the results will be based in the US Center for Diseases Control and Prevention Hepatitis B Serology Interpretation (available at <http://www.U.S.Center for Disease Control and Prevention.gov/hepatitis/HBV/HBVfaq.htm#general>).

Individuals with chronic or acute hepatitis B infection will not be eligible to participate. Hepatitis B susceptible participants will be offered hepatitis B vaccination according Ministry of Health of Peruvian guidelines.

6. Sexually transmitted infection testing

Syphilis screening testing will be conducted by RPR and confirmed by MHA-TP if reactive. Syphilis diagnosis will follow Ministry of Health of Peru guidelines. A positive leukocyte esterase test by a urine dipstick will trigger a microscopic examination. Further confirmation with a nucleic acid amplification test for *N. gonorrhoeae* and *C. trachomatis* will follow if a diagnosis of urethritis is made.

#### **7.4.3.7 Immunologic Studies**

1. CD4+/CD8+ T-cell subsets

A CD4+ T-lymphocyte percent of total lymphocytes and CD8+ T-lymphocyte percent of total lymphocytes should be performed in addition to the absolute CD4+ and CD8+ T cell counts at screening and for all visits at which CD4+/CD8+ T cell counts are required. Because of the diurnal variation in CD4+ and CD8+ cell counts, determinations for individual subjects should be obtained consistently in either the morning or the afternoon throughout the study, if possible.

NOTE: Each time a CD4+/CD8+ measurement is obtained, the local laboratory must perform a WBC and differential from a sample obtained at the same time.

#### **7.4.3.8 Virologic Studies**

1. Plasma HIV-1 RNA

All HIV-1 RNA testing will be performed using the Abbott *m2000 RealTime* System (Abbott Molecular) at the IMPACTA PERU Clinical Trials Unit Central Laboratory, which

is certified by the U.S. NIH/NIAID/DAIDS Virology Quality Assurance (VQA) Program. The baseline value will be the HIV-1 RNA level at the entry evaluation.

The results from the analysis of Plasma HIV-1 RNA for the visits 0, 12, 24, 36, and 48 will be available at the next follow-up visit to guide the medical management decision-making for each participant, according to the HIV management standards.

The plasma samples for RNA HIV-1 determination from visits 1, 2, 4, 6, 8, 16, and 20 will not be processed in real time. Since these determinations are exclusively research purposes, the samples will be processed at a later time.

2. **Phylogenetic Analyses**

HIV-1 sequencing and phylogenetic analysis will be performed at The University of Washington Molecular Genetics Laboratory

**7.4.3.9 Genotype**

HIV-1 genotype in stored samples will be performed by the University of Washington Virology Specialty Laboratory at the end of the study or when required per clinical judgment at time of suboptimal virologic response.

**7.4.3.10 Semen and Rectal Secretions**

Semen and rectal secretion specimens will occur according to the schedule of events as specified in Section 7.4.1. Samples will be initially processed and stored as stated in the Protocol Study Specific Procedures. HIV-1 viral load in semen and rectal secretions will be tested at the University of Washington Retrovirology Laboratory at the end of the study.

**7.4.3.11 Stored Plasma**

At all-time points for which an HIV-1 RNA level is required the remaining plasma after the HIV-1 RNA assay is performed will be stored.

**7.4.3.12 Hair.** This section has been created to describe the following:

The collection of a snip of hair (approximately 80 or 120 individual hairs) will be obtained from the scalp of the participants using a pair of scissors, as specified in section 7.4.1. If it is not possible to obtain hair from the scalp, then hair from face, extremities or pubic region may be obtained, also using a pair of scissors. The hair samples will be analyzed in ethyl glucuronide (marker for chronic alcohol consumption) and a commercially available kit will be used for the analysis of cocaine, marijuana, phencyclidine, amphetamines, and opioid consumption.

**7.4.3.12 Hair.** As a result of the above change, the following foot note has been added:

3 Drug Testing: A white paper of The American Society of Addiction Medicine. 2013.  
<http://www.asam.org/docs/default-source/public-policy-statements/drug-testing-a-white-paper-byasam.pdf>

**7.4.3.13 Questionnaires**

Interviews will either be administered by interviewers (monthly) or self-administered by participants (quarterly).

The AUDIT will be administered at the first visit only, along with a short questionnaire, including demographics, health literacy, and another short questionnaire.

A questionnaire (roughly 60 minutes) will be administered at the first study visit and then quarterly. It will contain several modules as follows:

1. Drug and alcohol use (drug use history, DAST 10, drinking expectancies);
2. Mental health and well being (RAND 12, Social support scale, Stigma scale, Stigma and disclosure, Partner notification, Intimate partner violence, 10 item CES-D, CID Mental health items on anxiety, Stress & Coping);
3. Medical care (Hospitalization and ER use, Barriers to care, Access to care, Self efficacy for ART use).

In addition, there will be a monthly interviewer-administered questionnaire containing the following items: Timeline Follow Back (alcohol use and sexual behavior), Visual analog scale for ART adherence, and Medication adherence program choices.

The Timeline Follow Back questionnaire includes questions on sexual partners. We will collect anonymous interview data about partners (including number of partners, type of partner [main, casual, anonymous], etc.). We will also counsel men on the need to inform recent sexual partners that they may have been exposed to HIV. Scripts have been developed to guide this process. In brief, all participants will be provided with intensive one-on-one partner notification counseling with a trained member of the staff. First party partner notification (notification of partners by the index HIV-infected MSM and transgender women) will be encouraged and supported by use of a printed referral card. Third party notification (notification by the provider that a person may have been exposed to HIV) will be offered as an option in situations where the participant does not want to or does not feel comfortable notifying their partner directly. All third party notifications will be anonymous (i.e., will not reveal participants' names or other identifying information). Any partners who wish to be tested for HIV will be offered free HIV testing at IMPACTA Barranco or IMPACTA San Miguel Clinical Research Site (the study sites).

**8 WARNINGS AND PRECAUTIONS**

**8.1 LACTIC ACIDOSIS/SEVERE HEPATOMEGALY WITH STEATOSIS**

Lactic acidosis and severe hepatomegaly with steatosis, including fatal cases, have been reported with the use of nucleoside analogs alone or in combination with other antiretrovirals. A majority of these cases have been in women. Obesity and prolonged nucleoside exposure may be risk factors. Particular caution should be exercised when administering nucleoside analogs to any patient with known risk factors for liver disease; however, cases have also been reported in patients with no known risk factors.

Treatment with co-formulated elvitegravir/cobicistat/emtricitabine/tenofovir disoproxil fumarate or co-formulated emtricitabine/tenofovir DF/efavirenz should be suspended in any patient who develops clinical or laboratory findings suggestive of lactic acidosis or pronounced hepatotoxicity (which may include hepatomegaly and steatosis even in the absence of marked transaminase elevations).

## **8.2 PATIENTS WITH HIV AND HBV COINFECTION**

It is recommended that all patients with HIV be tested for the presence of hepatitis B before initiating antiretroviral therapy. Co-formulated elvitegravir/cobicistat/emtricitabine/tenofovir disoproxil fumarate or co-formulated emtricitabine/tenofovir DF/efavirenz is not indicated for the treatment of chronic HBV infection and the safety and efficacy of co-formulated emtricitabine/tenofovir DF/efavirenz have not been established in patients co-infected with hepatitis B virus and HIV. Severe acute exacerbations of hepatitis B have been reported in patients after the discontinuation of emtricitabine and tenofovir DF. Hepatic function should be closely monitored with both clinical and laboratory follow-up for at least several months in patients who discontinue co-formulated elvitegravir/cobicistat/emtricitabine/tenofovir disoproxil fumarate or co-formulated emtricitabine/tenofovir DF/efavirenz and are co-infected with HIV and HBV.

HIV-1/hepatitis B co-infected individuals will not be enrolled in this study.

## **8.3 PSYCHIATRIC SYMPTOMS**

Serious psychiatric adverse experiences have been reported in patients treated with efavirenz. In controlled trials of 1008 patients treated with regimens containing efavirenz for a mean of 2.1 years and 635 patients treated with control regimens for a mean of 1.5 years, the frequency of specific serious psychiatric events among patients who received efavirenz or control regimens, respectively, were: severe depression (2.4%, 0.9%), suicidal ideation (0.7%, 0.3%), nonfatal suicide attempts (0.5%, 0%), aggressive behavior (0.4%, 0.5%), paranoid reactions (0.4%, 0.3%), and manic reactions (0.2%, 0.3%). When psychiatric symptoms similar to those noted above were combined and evaluated as a group in a multifactorial analysis of data from Study A1266006 (006), treatment with efavirenz was associated with an increase in the occurrence of these selected psychiatric symptoms. Other factors associated with an increase in the occurrence of these psychiatric symptoms were history of injection drug use, psychiatric history, and receipt of psychiatric medication at study entry; similar associations were observed in both the efavirenz and control treatment groups. In Study 006, onset of new serious psychiatric symptoms occurred throughout the study for both efavirenz-treated and control-treated patients. One percent of efavirenz-treated patients discontinued or interrupted treatment because of one or more of these selected psychiatric symptoms. There have also been occasional post-marketing reports of death by suicide, delusions, and psychosis-like behavior; although a causal relationship to the use of efavirenz cannot be determined from these reports.

Patients with serious psychiatric adverse experiences should seek immediate medical evaluation to assess the possibility that the symptoms may be related to the use of efavirenz, and if so, to determine whether the risks of continued therapy outweigh the benefits

#### **8.4 NERVOUS SYSTEM SYMPTOMS**

Fifty-three percent of patients receiving efavirenz in controlled trials reported central nervous system symptoms compared to 25% of patients receiving control regimens. These symptoms included dizziness (28.1%), insomnia (16.3%), impaired concentration (8.3%), somnolence (7.0%), abnormal dreams (6.2%), and hallucinations (1.2%). Other reported symptoms were euphoria, confusion, agitation, amnesia, stupor, abnormal thinking, and depersonalization. The majority of these symptoms were mild-moderate (50.7%); symptoms were severe in 2.0% of patients. Overall, 2.1% of patients discontinued therapy as a result. These symptoms usually begin during the first or second day of therapy and generally resolve after the first 2–4 weeks of therapy. After 4 weeks of therapy, the prevalence of nervous system symptoms of at least moderate severity ranged from 5% to 9% in patients treated with regimens containing efavirenz and from 3% to 5% in patients treated with a control regimen. Patients should be informed that these common symptoms were likely to improve with continued therapy and were not predictive of subsequent onset of the less frequent psychiatric symptoms. Dosing at bedtime may improve the tolerability of these nervous system symptoms.

Analysis of long-term data from Study 006, (median follow-up 180 weeks, 102 weeks, and 76 weeks for patients treated with efavirenz + zidovudine + lamivudine, efavirenz +indinavir, and indinavir + zidovudine + lamivudine, respectively) showed that, beyond 24 weeks of therapy, the incidences of new-onset nervous system symptoms among efavirenz-treated patients were generally similar to those in the indinavir-containing control arm. Patients receiving co-formulated emtricitabine/tenofovir DF/efavirenz should be alerted to the potential for additive central nervous system effects when co-formulated emtricitabine/tenofovir DF/efavirenz is used concomitantly with alcohol or psychoactive drugs.

Patients who experience central nervous system symptoms such as dizziness, impaired concentration, and/or drowsiness should avoid potentially hazardous tasks such as driving or operating machinery.

#### **8.5 NEW ONSET OR WORSENING RENAL IMPAIRMENT**

Renal impairment, including cases of acute renal failure and Fanconi syndrome (renal tubular injury with severe hypophosphatemia), has been reported with the use of tenofovir DF, and it's formulations. Estimated creatinine clearance, urine glucose and urine protein should be documented in all patients prior to initiating therapy. Initiation of co-formulated elvitegravir/cobicistat/emtricitabine/tenofovir disoproxil fumarate in patients with estimated creatinine clearance below 70 mL per minute is not recommended.

Co-formulated elvitegravir/cobicistat/emtricitabine/tenofovir disoproxil fumarate and co-formulated emtricitabine/tenofovir DF/efavirenz should be avoided with concurrent or recent use of a nephrotoxic agent (e.g., high-dose or multiple non-steroidal anti-inflammatory drugs (NSAIDs)). Cases of acute renal failure after initiation of high dose or multiple NSAIDs have been reported in HIV-infected patients with risk factors for renal dysfunction who appeared

stable on tenofovir DF. Some patients required hospitalization and renal replacement therapy. Alternatives to NSAIDs should be considered, if needed, in patients at risk for renal dysfunction. Persistent or worsening bone pain, pain in extremities, fractures and/or muscular pain or weakness may be manifestations of proximal renal tubulopathy and should prompt an evaluation of renal function in at-risk patients.

Routine monitoring of estimated creatinine clearance, urine glucose, and urine protein should be performed during co-formulated elvitegravir/cobicistat/emtricitabine/tenofovir disoproxil fumarate therapy in all patients. Additionally, serum phosphorus should be measured in patients at risk for renal impairment.

Although cobicistat (a component of STRIBILD) may cause modest increases in serum creatinine and modest declines in estimated creatinine clearance without affecting renal glomerular function, patients who experience a confirmed increase in serum creatinine of greater than 0.4 mg per dL from baseline should be closely monitored for renal safety. The emtricitabine and tenofovir DF are primarily excreted by the kidney. Co-formulated elvitegravir/cobicistat/emtricitabine/tenofovir disoproxil fumarate and co-formulated emtricitabine/tenofovir DF/efavirenz should be discontinued if estimated creatinine clearance declines below 50 mL per minute as dose interval adjustment required for emtricitabine and tenofovir DF cannot be achieved with the fixed-dose combination tablet.

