### **6.3 STEP 3**

#### **6.3.1 Regimens, Administration, and Duration**

##### **6.3.1.1 Regimen**

Those participants, who have initiated their participation in the study before the approval of **Amendment Letter #1** in this study protocol, will continue their participation as originally programmed.

Once the **Amendment Letter #1** is approved for this study protocol, the participants who are eligible for Step 3 will be given treatment the following way:

- Those people diagnosed with **acute HIV infection** will be offered immediate ART (just at time of the enrollment visit or during the next 48 to 72 hours) for the duration of 48 weeks.

Weeks 0-48: Co-formulated elvitegravir/cobicistat/emtricitabine/tenofovir disoproxil fumarate (or co-formulated emtricitabine/tenofovir DF/efavirenz) orally once daily.

Those people diagnosed with recent HIV infection will be randomized to one of the following arms:

1. Arm 1:

Weeks 0-48: Co-formulated elvitegravir/cobicistat/emtricitabine/tenofovir disoproxil fumarate (or co-formulated emtricitabine/tenofovir DF/efavirenz) orally once daily.

2. Arm 2:

Week 0-24: No treatment unless Peruvian criteria for initiation of treatment are met.

Week 25-48: Co-formulated elvitegravir/cobicistat/emtricitabine/tenofovir disoproxil fumarate (or co-formulated emtricitabine/tenofovir DF/efavirenz) orally once daily.

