Chemistry/LFT				X		X	X			X							X	
Lipid panel	X***						X			X							X	
Urinalysis	X			X			X			X							X	
Hepatitis B serology																		
STI testing	X						X			X							X	
CD4+/CD8+ cells count	X			X			X			X					X		X	
Plasma HIV-1 RNA	X	X	X	X	X	X	X	X	X	X					X		X	
Semen and rectal secretion collection	X	X	X	X	X	X	X	X	X	X					X		X	
Screening questionnaire - Demographics	X																	
AUDIT	X																	
Interviewer – Monthly questionnaire*	X			X		X	X	X	X				X	X	X	X	X	
Quarterly questionnaire**	X					X			X					X			X	
Pharmacy Refills				X		X	X	X	X				X	X	X	X	X	
Hair Sample	X					X			X					X			X	
Blood volumes (ml) for participants with immediate treatment	160	60	60	71.5	10	121.5	21.5	110	10	121.5	50	50	50	100	13	100	0	121.5
Blood volumes (ml) for participants with deferred treatment	230	60	60	71.5	0	201.5	21.5	190	10	201.5	50	50	50	100	13	100	0	121.5

\*Monthly interviewer-administered questionnaire containing: Timeline Follow Back (alcohol use and sexual behavior), Visual analog scale for ART adherence, and Medication adherence program choices

\*\*Quarterly questionnaire containing: Drug and alcohol use (drug use history, DAST 10, drinking expectancies); Mental health and wellbeing (RAND 12, Social support scale, Stigma scale, Stigma and disclosure, Partner notification, Intimate partner violence, 10 item CES-D, CID Mental health items on anxiety, stress & coping; Medical care (Hospitalization and ER use, Barriers to care, Access to care, Self-efficacy for ART use). \*\*\* These will be done within 72 hours.

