#### **9.2.6 Hypophosphatemia**

For Grade 1 and Grade 2 hypophosphatemia, phosphorus should be repeated as soon as possible (within 2 weeks is optimal), and tenofovir DF may be continued without other signs of renal tubular acidosis at the discretion of the site investigator.

For asymptomatic Grade 3 decreases in phosphorus, subjects may either substitute another nucleoside reverse transcriptase inhibitor (NRTI) for tenofovir DF, or may remain on tenofovir DF with the following caveats. Subjects should be treated with oral phosphate supplements and phosphorus levels should be re-tested weekly until phosphorus returns to Grade 2 or better. If Grade 3 or worse phosphorus levels persist, tenofovir DF should be discontinued and another NRTI should be substituted. If Grade 4 hypophosphatemia occurs, tenofovir DF should be changed to an alternative NRTI in consultation with the Protocol Chair, and serum phosphorus levels should be followed weekly until resolution to Grade 2 or better.

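### A participant who starts deferred ART at week 24 has one scheduled on-treatment creatinine and urinalysis, at the week-48 final visit, because the safety-laboratory calendar follows study week and not time on ART

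*Combined protocol and SAP*

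**What the plan says.** **Treatment timing.** For Arm 2, Section 6.3.1.1 gives "Week 0-24: No treatment unless Peruvian criteria for initiation of treatment are met", followed by study ART to week 48. Both co-formulated regimens contain tenofovir DF (Section 6.3.2).

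**Monitoring.** Section 8.5 asks for pre-therapy documentation: "Estimated creatinine clearance, urine glucose and urine protein should be documented in all patients prior to initiating therapy". It then asks for on-therapy monitoring: "Routine monitoring of estimated creatinine clearance, urine glucose, and urine protein should be performed during co-formulated elvitegravir/cobicistat/emtricitabine/tenofovir disoproxil fumarate therapy in all patients". That sentence names Stribild only and gives no interval. Section 8.5 asks for serum phosphorus only in patients at risk of renal impairment.

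**Action rules.**
- Section 8.5 stops either fixed-dose tablet if estimated clearance falls below 50 mL/min.
- For patients on the cobicistat-containing tablet, it says those with a "confirmed increase in serum creatinine of greater than 0.4 mg per dL from baseline should be closely monitored for renal safety".
- Section 9.2.5 acts on a confirmed creatinine more than 1.5-fold above baseline, where baseline is the mean of the screening and entry values. The repeat is preferably within one week.
- Section 9.2.6 begins one rule "For asymptomatic Grade 3 decreases in phosphorus, subjects may either substitute another nucleoside reverse transcriptase inhibitor". For Grade 1 and 2 values it says "phosphorus should be repeated as soon as possible (within 2 weeks is optimal").

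**Where the values come from.** The chemistry panel in Section 7.4.3.6 is "Serum amylase, lipase, bicarbonate, phosphorus, creatinine, AST (SGOT), ALT (SGPT), alkaline phosphatase". Urine glucose and protein would come from the urinalysis dipstick. Section 7.4.2.2 ties on-study evaluations to the tables in Section 7.4.1, chosen by whether enrollment came before or after Amendment Letter #1.

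**The concern.** The tables count from enrollment, which suits Arm 1 because its ART also starts at enrollment. For Arm 2 the dense early chemistry (weeks 4, 8 and 12) falls in the untreated period, and the week-24 panel coincides with ART start. What follows is the sparse part of the calendar, which in Arm 1 comes only after four on-treatment checks.

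The action rules work in weeks, while the first scheduled value after a week-24 start comes about 24 weeks later. Section 8.5 prompts a renal evaluation for bone or muscle symptoms in at-risk patients. That cannot replace scheduled tests, since Section 9.2.6 is written partly for asymptomatic low phosphorus.

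An abnormality first seen at week 48 would still be followed (Section 12.8). But substitute drugs are supplied only while the participant is in the study (Section 6.3.7.3), and ART then comes from other sources (Section 6.3.1.3). The safety plan in Section 12.7 also asks whether the arms differ in toxicity, and on-treatment checks are spaced very differently between them.

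**Working it through.** The plan states no figure on this point, so the check is a reading of the two Section 7.4.1 tables.

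**Chemistry row.** In the original table the row fills all 16 week columns and marks weeks 4, 8, 12, 24 and 48. In the amended table it marks weeks 4, 8, 12 and 24, plus a last mark that appears one column early, under week 44. The row "Blood volumes (ml) for participants with deferred treatment" settles that mark: 0 mL at week 44 and 121.5 mL at week 48. Read literally as week 44, the gap would still be 20 weeks.

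**Blood volumes as a cross-check.** A draw with chemistry is 11.5 mL larger than one without (original table, week 8 minus week 6: 21.5 − 10 = 11.5; this step also covers the CBC). In every volume row a figure ending in .5 occurs only at weeks 4, 8, 12, 24 and 48.
- Original: 0 mL at weeks 28, 32, 40 and 44, and 13 mL at week 36.
- Amended, deferred: 50, 50, 50, 100, 13, 100 and 0 mL at weeks 25, 26, 28, 32, 36, 40 and 44. At the weeks shared with the original table, these are the original figures plus round 50 or 100 mL draws.

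**Urinalysis row.** Both tables mark week 24 and then only the last visit. Volumes cannot check this row.

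**Scheduled looks by time on ART (amended table).**

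| | Arm 1 | Arm 2, start at week 24 |
|---|---|---|
| First chemistry | 4 weeks | 24 weeks |
| Chemistry looks in first 24 weeks of ART | 4 (4, 8, 12, 24) | 1 (24) |
| Urinalysis looks in first 24 weeks of ART | 3 (4, 12, 24) | 1 (24) |

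**Early starters (Section 4.2).** A start at week 12, 16 or 20 has its first on-ART chemistry at week 24, which is 12, 8 or 4 weeks later. They are partly covered.

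**Illustration of detection.** Assume onset is uniform over the first 24 weeks of ART and the abnormality lasts d weeks. The share caught by scheduled chemistry is the part of the 24 weeks lying within d weeks before a look.

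| d | Arm 1 | Arm 2 |
|---|---|---|
| 4 | 16/24 = 67% | 4/24 = 17% |
| 8 | 20/24 = 83% | 8/24 = 33% |
| 12 | 24/24 = 100% | 12/24 = 50% |

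If the abnormality persists, both arms catch it and only the delay differs. The mean wait is (12 × 2 + 12 × 6)/24 = 4 weeks in Arm 1 (maximum 12) against 12 weeks in Arm 2 (maximum 24). Over Arm 1's full 48 weeks on ART its mean wait is (24 × 4 + 24 × 12)/48 = 8 weeks, because its weeks 24 to 48 are untested too.

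**The case against.** **No rule is broken.** A reader might infer that the monitoring in Section 8.5 is not delivered at all during deferred ART, or that the schedule contradicts it. The documents do not support that. Section 8.5 gives no interval, and the week-48 panel is one on-treatment check. The plan also accepts 24 weeks between panels in Arm 1 after week 24. The sentence does not cover Atripla, and phosphorus is asked for only in at-risk patients. Entry criteria already require clearance above 70 mL/min and phosphorus above 2.0 mg/dL, and exclude ongoing nephrotoxic systemic agents. All of this stands, and it limits the point to weak delivery.

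**The tables are damaged, and a missing mark need not mean a missing test.** Several rows are visibly shifted. Chemistry has no week-0 mark although Section 9.2.5 uses an entry creatinine, the hepatitis B row is empty although testing is required, and weeks 25 and 26 show blood volumes with no procedure marked. This stands in part. The urinalysis claim rests on absent marks alone. For chemistry, the volumes agree with the marks in both tables, although at amended weeks 28, 32 and 40 they support the reading and do not prove it.

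**Tests can be ordered anyway.** Clinical contact continues about every four weeks from week 28, clinicians may test when they see cause, and the Study Specific Procedures, which were not available, may add panels. None of this puts a test in the protocol.

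**The percentages are constructed.** This stands. Onset and duration are assumed, and the low Arm 2 figures need an abnormality that resolves while the drug continues.

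**Conclusion.** The gap holds in limited form. For an Arm 2 participant starting at week 24, the protocol schedules one on-treatment creatinine and urinalysis, at the final visit, against chemistry at 4, 8, 12 and 24 weeks of ART in Arm 1. The 50 mL/min rule and Sections 9.2.5 and 9.2.6, which apply to tenofovir DF in either regimen, then depend on unscheduled tests in the first months of deferred ART.

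This rests on three readings: that the last mark in the amended table belongs to week 48, that unmarked visits carry no panel, and that nothing outside the protocol adds one. The first is well supported by the volumes. The detection figures are illustrative only: the documents give no event rate, onset pattern or duration, so no statement about harm follows. The viral-load endpoint is not affected. The change is worth making because it is specific, serves participant safety and costs little.

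**What to change.** 1. For Arm 2, add Chemistry/LFT and urinalysis at the existing week 28, 32 and 36 visits. For early starters under Section 4.2, use the visits nearest 4, 8 and 12 weeks after actual ART start. With the week-48 panel, a week-24 starter then has chemistry at 4, 8, 12 and 24 weeks of ART, as in Arm 1.
2. For Arm 2, use the last pre-ART creatinine (week 24 for those starting then) as the reference for the 1.5-fold rule in Section 9.2.5 and the 0.4 mg/dL rule in Section 8.5. The week-24 chemistry and urinalysis also supply the pre-therapy documentation that Section 8.5 asks for.
3. Chemistry looks by arm would go from five each to eight in Arm 2 (5 + 3) against five in Arm 1. Count Grade 3 or higher laboratory values by arm at the common weeks only (4, 8, 12, 24, 48) and list the added panels separately. If toxicity is compared by time on ART, use matched looks at 4, 8, 12 and 24 weeks.

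**Cost.** Three routine panels and dipsticks per deferred participant, plus a protocol amendment with ethics review.
- Number affected, assuming 1:1 allocation and half of 75 to 125 recent infections still to enroll (Section 4.1 says roughly half are enrolled): 75/4 ≈ 19 to 125/4 ≈ 31 participants, or about 56 to 94 panels.
- Blood: at most 3 × 11.5 = 34.5 mL each. The amended schedule already draws 50 + 50 + 50 + 100 + 13 + 100 = 363 mL at weeks 25 to 40, so this adds 34.5/363 = 9.5%.
- Anyone still on the original schedule would need new draws at weeks 28 and 32, where none is taken now.

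The change leaves Arm 1's own gap from week 24 to week 48 as it is.
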